h. **P-values** Adjusted p-values were compared with the Family Wise Error Rate (FWER) to conclude on whether the null hypotheses were rejected or not. FWER for Family 1 is initially set to be 1/3 of the full alpha, which is rounded to 0.017. The FWER for Family 2 is 0.033 and the initial FWER is 0 for Family 3, 4 and 5. No multiplicity adjustment was performed within a family. Within family 1 all thirteen antigens were tested with the full FWER for family 1. If one or more test fail to reject the hypothesis for the antigen, family 1 fails. Consequently the alpha of family 1 will not be propagated (see bullet h. below).

i. Preparing for testing Family 2 **and 3 to 5**, percentages were obtained by dichotomizing the normal random sets that were generated at step b, by applying the cut-off of LLOQ value for post 3rd or a cut-off of 4 at post 4th. By applying a cut-off of 4 to the GMRs at post-4th this will generate a percentage of subjects who had a 4-fold increase for their GMT value at post-4th compared to pre-4th, which is an approximation of the percentage of 4-fold increase using LOD and LLOQ values. ~~A check step has been performed by comparing the percentages generated from this step with the true percentages observed from clinical trials. The results were comparable.~~ Per time point, composite endpoint was derived by looking into each subject if the titer is above the cut-off for all 4 individual strains and if it is then this subject is counted as "1". Otherwise the subject is counted as "0".

j. For each of the ten percentages for rMenB+OMV NZ (4 individual strains and 1 composite endpoint at post-3rd and post-4th) the lower confidence limit was generated by fitting the binomial distribution with the percentage obtained from the previous step and alpha that has been assigned or propagated to the family. If the lower confidence limit is greater or equal to the sufficiency margin, then the null hypothesis is rejected for the single test. For Family 2 and 3, it is required to reject the null hypothesis for each and all of strain M14459, 96217, ~~and~~ NZ98/254, **M10713, and the composite endpoint** to be able to claim the success of the family. ~~For family 4 and 5, it is required to reject the null hypothesis for both M07-0241084 and the composite endpoint to be able to claim the family success.~~

k. Testing of Family 2: with the given FWER, if the LCL is greater or equal to 0.7 for each of strain M14459, 96217 and NZ98/254, **greater or equal to 0.66 for strain M10713, and greater or equal to 0.48 for the composite endpoint**, then Family 2 is claimed for success. The FWER for Family 2 is set up as 2/3 of the full alpha, which is rounded to ~~0.33~~ **0.033**.

l. Testing of Family 3: with the given FWER, if the LCL is greater or equal to 0.6 for each of strain M14459, 96217 and NZ98/254, **greater or equal to 0.55 for strain M10713, and greater or equal to 0.43 for the composite endpoint**, then Family 3 is claimed for success. ~~Propagate the FWER from Family 3 to Family 4 and continue to test Family 4. Otherwise, if Family 3 fails, then stop testing globally.~~

m. ~~Testing of Family 4: with the given FWER, if the LCL is greater or equal to 0.5 for strain M07-0241084 and the LCL is greater or equal to 0.4 for the composite endpoint, then Family 4 is claimed for success. Propagate FWER from Family 4 to Family 5 and continue to test Family 5. Otherwise, if Family 4 fails, then stop testing globally.~~

n. ~~Testing of Family 5: with the given FWER, if the LCL is greater or equal to 0.12 for strain M07-0241084 and the LCL is greater or equal to 0.1 for the composite endpoint, then Family 5 is claimed for success. Otherwise, Family 5 fails.~~

Table 18 Two-sided 80% Upper Confidence Limit of Standard Deviations

	80% UCL of SDs	
rMenB+OMV NZ strains	Post 4 th vaccination (SDs of GMR)	Post 3 rd vaccination (SDs of GMT)
M14459	0.54372	0.32221
96217 ²	0.77760	0.36900
NZ98/254	0.51794	0.51967
M07-0241084 M10713	0.66918	0.39959 0.522
PCV13 antigen ¹	Post 3 rd vaccination (SDs of GMC)	
1	0.36629	
3	0.41572	
4	0.34261	
5	0.43567	
6A	0.39552	
6B	0.44974	
7F	0.34352	
9V	0.32548	
14	0.32445	
18C	0.33550	
19A	0.24439	
19F	0.45638	
23F	0.37567	

¹. Estimated SDs for PCV13 antigens are the upper confidence limit of 2-sided 80% CI of back-calculated SDs, based on information (degree of freedom, 95% CI) provided on table 17 of *Prevnar13 Package Insert* (dated on July 2016) and assuming the underlying SDs fulfill a t-distribution.

² The SD for 96217 at post-4th vaccination GMR is not available and hence assumed the SD of GMR from Strain GB394.

³ For strain M07-0241084 as no pre-4th vaccination data available, GMR was calculated by post-4th/post-3rd vaccination.

Table 20 Limit of Detection and Lower Limit of Quantitation for rMenB+OMV NZ strains

rMenB+OMV NZ strains	LOD	LLOQ
M07-024180 M10713	43	4 16
NZ98/254	4	6
M14459	3	5
96217	6	15

LOD: lower limit of detection, LLOQ: lower limit of quantitation.

Note: **Other than for strain M10713, these LODs and LLOQs were cited from the latest lab assay pre-validation report released in 2018Q2-2017. For strain M10713, the LOD and LLOQ are to be determined. They are subject to change upon CBER's potential comments on the validation plan.**

b. The percentage of subjects with titers \geq LLOQ is more than or equal to 60% for strain M14459, 96217 and NZ98/254, and more than or equal to 42%–55% for strain M07-0241084 **M10713**, and more than or equal to 40%–43% for all 4 rMenB+OMV NZ strains at one month post 3rd vaccination.

- c. Percentage of subjects with 4-fold increase is more than or equal to 70% for strain M14459, 96217 and NZ98/254, and more than or equal to ~~50%66%~~ for strain ~~M07-0241084~~**M10713**, and more than or equal to ~~40%48%~~ for all four rMenB+OMV NZ strains , at one month post 4th vaccination.

Section 9.7.1 Within groups assessment:

For each study group, at each timepoint that a blood sample result is available, the following endpoints will be assessed related to MenB strains and PCV13 strains:

- the percentage of subjects with hSBA titers \geq LLOQ for each of the M14459, 96217, NZ98/254 and ~~M07-0241084~~**M10713** test strains
- the percentage of subjects with hSBA titers \geq LLOQ for all strains combined (composite endpoint)
- the percentage of subjects with hSBA titers ≥ 5 and ≥ 8 for each of the M14459, 96217, NZ98/254 and ~~M07-0241084~~**M10713** test strains
- the percentage of subjects with 4-fold increase at post-4th (from ~~post-3rd pre-4th~~) for each of the M14459, 96217, NZ98/254 and ~~M07-0241084~~**M10713** test strains.

9.7.3.1 Statistical Hypotheses:

In total 23 hypotheses will be tested for the primary objectives. A step-wise statistical approach will be used for the 23 statistical tests. The hypotheses will be grouped into ~~five~~ **three** families, based on the different immunogenicity objectives:

Family 1:13 statistical hypotheses related to non-inferiority of PCV13 with rMenB+OMV NZ as measured by the GMCs of the 13 PCV13 antigens, after the 3rd vaccination.

Family 2: ~~3~~ **5** statistical hypotheses related to sufficiency objective on percentage of subjects with 4-fold increase at post 4th dose (from pre-4th dose) for each of the ~~three~~ **four** strains M14459, 96217, NZ98/254, **and M10713, and the composite endpoint**

Family 3: ~~3~~ **5** statistical hypotheses related to sufficiency objective on percentage of subjects with hSBA titers \geq LLOQ at post 3rd dose for each of the ~~three~~ **four** strains M14459, 96217, NZ98/254, **and M10713, and the composite endpoint.**

Family 4: ~~2~~ statistical hypotheses related to sufficiency objective on percentage of subjects with 4-fold increase at post 4th dose (from pre-4th dose) for strain ~~M07-021084~~ and for all strains combined

Family 5: ~~2~~ statistical hypotheses related to sufficiency objective on percentage of subjects with hSBA titers \geq LLOQ at post 3rd dose for strain ~~M07-021084~~ and for all strains combined

Families 2 and ~~5~~ **3** are related to the “*sufficiency of the immune response to rMenB+OMV NZ*” objective at one month post-3rd-4th dose and one month post-3rd 4th dose, **respectively**.

Family 2: Percentage of subjects with 4-fold increase for each of the **three four** strains (M14459, 96217, NZ98/254, **M10713**) and the composite endpoint, post-4th

Sufficiency will be claimed for each of the **4** strains **and the composite endpoint**, separately, if the following null hypothesis will be rejected:

$$H_{02j}: P_{Aj} < A_j \text{ vs. } H_{12j}: P_{Aj} \geq A_j,$$

where P_{Aj} denotes the percentage of subjects with 4-fold increase at one month after the 4th vaccination (from pre-4th dose) for strain j , ($j=1, 2, 3, 4, \text{ and composite}$), which is assumed to be at least 90% for each of the three strains M14459, 96217, and NZ98/254, **72% for strain M10713, and 54% for the composite endpoint (estimate based on assumption of 25% correlation)**. A_j represents the level of sufficient immune response for each of the **three four** strains **and composite endpoint**. The immune response at one month following the 4th vaccination, will be sufficient for rMenB+OMV against each individual strain if the lower limit of the adjusted CI for the percentage of subjects with 4-fold increase is $\geq 70\%$ for strains M14459, 96217, NZ98/254, **$\geq 66\%$ for strain M10713, and $\geq 48\%$ for the composite endpoint**.

Family 3: Percentage of subjects with hSBA \geq LLOQ for each of the **four** strains (M14459, 96217, NZ98/254, **M10713**) and the composite endpoint, post-3rd

Sufficiency will be claimed for each of the 4 strains, separately, if the following null hypothesis will be rejected:

$$H_{03j}: P_{Aj} < A_j \text{ vs. } H_{13j}: P_{Aj} \geq A_j,$$

where P_{Aj} denotes the percentage of subjects hSBA \geq LLOQ at one month after the 3rd vaccination for strain j , ($j=1, 2, 3, 4, \text{ and composite}$), which is assumed to be at least 90% for strains M14459 and 96217, 80% for NZ98/254, **61% for strain M10713, and 49% for the composite endpoint**. A_j represents the level of sufficient immune response for each of the **four** strains **and composite endpoint (estimate based on assumption of 25% correlation)**. The immune response at one month following the 3rd vaccination, will be sufficient for rMenB+OMV NZ against each individual strain if the lower limit of the adjusted CI for the percentage of subjects with hSBA titer \geq LLOQ is $\geq 60\%$ for strains M14459, 96217, NZ98/254, **$\geq 55\%$ for strain M10713, and $\geq 43\%$ for the composite endpoint**.

Family 3: Percentage of subjects with hSBA \geq LLOQ for each of the **three four** strains (M14459, 96217, NZ98/254, **M10713**) and the composite endpoint, post-3rd

Sufficiency will be claimed for each of the **3** 4 strains, separately, if the following null hypothesis will be rejected:

$$H_{03j}: P_{Aj} < A_j \text{ vs. } H_{13j}: P_{Aj} \geq A_j,$$

where P_{Aj} denotes the percentage of subjects hSBA \geq LLOQ at one month after the 3rd vaccination for strain j , ($j=1, 2, 3, 4, \text{ and composite}$), which is assumed to be at least 90% for strains M14459 and 96217, and 80% for NZ98/254, **61% for strain M10713, and 49% for the composite endpoint**. A_j represents the level of sufficient immune response for each of the **three four** strains **and composite endpoint**. The immune response at one

month following the 3rd vaccination, will be sufficient for rMenB+OMV NZ against each individual strain if the lower limit of the adjusted CI for the percentage of subjects with hSBA titer \geq LLOQ is \geq 60% for strains M14459, 96217, NZ98/254, **\geq 55% for strain M10713, and \geq 43% for the composite endpoint.**

Family 4: Percentage of subjects with 4 fold increase for strain M07-0241084 and for the four strains combined, post-4th

Sufficiency will be claimed, if the following null hypothesis will be rejected:

$$H_{04j} : P_{Aj} < A_j \text{ vs. } H_{14j} : P_{Aj} \geq A_j;$$

where P_{Aj} denotes the percentage of subjects with 4 fold increase at one month after the 4th vaccination for strain M07-0241084 ($j=1$) and for the composite endpoint with all 4 strains combined ($j=2$), which are assumed to be 60% and 45% respectively. A_j represents the sufficient level for this composite endpoint, and is set to 50% for A_1 and 40% for A_2 . The immune response at one month following the 4th vaccination, will be sufficient for M07-0241084, if the lower limit of the adjusted CI for the percentage of subjects with 4 fold increase for M07-0241084 is \geq 50%. The immune response at one month following the 4th vaccination, will be sufficient for rMenB+OMV NZ for all strains combined, if the lower limit of the adjusted CI for the percentage of subjects with 4 fold increase for all strains combined is \geq 40%.

Family 5: Percentage of subjects with hSBA \geq LLOQ for strain M07-0241084 and for the four strains combined, post 3rd

Sufficiency will be claimed, if the following null hypothesis will be rejected:

$$H_{05j} : P_{Aj} < A_j \text{ vs. } H_{12j} : P_{Aj} \geq A_j;$$

where P_{Aj} denotes the percentage of subjects with hSBA \geq LLOQ at one month after the 3rd vaccination for strain M07-0241084 ($j=1$) and for the composite endpoint with all 4 strains combined ($j=2$), which are assumed to be 18% and 15% respectively. A_j represents the sufficient level for this composite endpoint, and is set to 12% for A_1 and 10% for A_2 . The immune response at one month following the 3rd vaccination, will be sufficient for M07-0241084, if the lower limit of the adjusted CI for the percentage of subjects with hSBA titer \geq LLOQ for M07-0241084 is \geq 12%. The immune response at one month following the 3rd vaccination, will be sufficient for rMenB+OMV NZ for all strain combined, if the lower limit of the adjusted CI for the percentage of subjects with hSBA titer \geq LLOQ for all strains combined is \geq 10%.

The initial α is 0.0167 (2-sided) for Family 1 and 0.033 (2-sided) for Family 2, while it is zero for all the other families **family 3**.

Step 1: Family 1 and Family 2

- i. Start test Family 1 and Family 2 as the first step. Within Family 1, the Bonferroni-Holm method will be applied to correct for multiplicity.

- For testing Family 1 the hypotheses per antigen the p-values will be obtained from an ANOVA model, with vaccination group and center as independent variables and log transformed titers/concentrations as response variable. ~~P-values will be adjusted by the Bonferroni Holm method, new (Bonferroni stepdown) p-values will be generated and outputted.~~
- The null hypotheses will be rejected if the ~~new, for multiplicity adjusted~~ p-values < FWER **for all thirteen antigens**.
- For testing Family 2, if the lower limits of the 2-sided ~~96.96~~ 98.33% CIs are greater or equal to the sufficiency margins for each of the ~~three~~ **four** strains **and composite endpoint**, then Family 2 is successful. Otherwise, Family 2 fails.

ii. If Family 1 had succeeded and Family 2 not, then propagate $\frac{1}{2}$ FWER from Family 1 to Family 3 and the other $\frac{1}{2}$ FWER to Family 2, and re-test Family 2 with the new FWER which is the sum of the original FWER from Family 2 plus the $\frac{1}{2}$ of FWER from Family 1. If the null hypothesis were rejected during the 2nd time test, then claim the success of Family 2 and propagate full FWER to Family 3; otherwise Family 2 fails and proceed with Family 3 testing with the $\frac{1}{2}$ of FWER propagated from Family 1.

iii. If Family 2 had succeeded and Family 1 not, then propagate $\frac{1}{2}$ FWER from Family 2 to Family 3 and the other $\frac{1}{2}$ FWER to Family 1, and re-test Family 1 with the new FWER which is the sum of the original FWER from Family 1 plus the $\frac{1}{2}$ of FWER from Family 2. If the null hypothesis were rejected during the 2nd time test, then claim the success of Family 1 and propagate full FWER to Family 3; otherwise Family 1 fails and proceed with Family 3 testing with the $\frac{1}{2}$ of FWER propagated from Family 2.

iv. If both Family 1 and Family 2 had succeeded, then the FWER from both families were propagated to Family 3, and proceed to test Family 3;

v. If both Family 1 and Family 2 had failed, then no FWER will be propagated to Family 3, and we stop the testing globally and success can be claimed on none of the ~~five~~ **three** families.

Step 2: Family 3:

~~If all null hypotheses are rejected, the propagate full FWER to Family 4; otherwise stop testing globally, and success can be claimed for Family 1 and/or Family 2 whichever was successful in Step 1.~~

Step 3: Family 4:

~~If all null hypotheses are rejected, the propagate full FWER to Family 5; otherwise stop testing globally, and success can be claimed for Family 3, as well as for Family 1 and/or Family 2 whichever was successful in Step 1.~~

Step 4-2: Family 5-3:

If all null hypotheses are rejected, then propagate 1/2 FWER to Family 1 and Family 2 respectively, and success can be claimed for Family 3, ~~Family 4 and Family 5~~ as well as for Family 1 and/or Family 2 whichever was successful in Step 1; otherwise stop testing globally, and success can be claimed for ~~Family 3 and Family 4, as well as for~~ Family 1 and/or Family 2 whichever was successful in Step 1.

Step 53: Family 1 or Family 2:

In case one of Family 1 and Family 2 failed in step 1, with the alpha passed down by Family 53, it is possible to re-test the family that failed once and again test it with $\frac{1}{2}$ FWER from Family 53. If all null hypotheses are rejected, then success can be claimed for this family as well.

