All AEs which do not fall into these categories are defined as non-serious. It should be noted that a severe AE need not be serious in nature and that an SAE need not, by definition, be severe. All SAEs will be evaluated by the investigator for relationship of the event to study vaccine.

7.1.3. **Solicited adverse events**

The term “reactogenicity” refers to solicited signs and symptoms (“solicited adverse events”) occurring in the hours and days following a vaccination, to be collected by the parent(s)/LAR(s) for 7 consecutive days (with ongoing solicited AEs collected until resolution or day 30, whichever occurs first), using a pre-defined Subject Diary.

Reactogenicity will be collected from all subjects after each vaccination visit (study Days 1, 61, 121 and 301). In addition, specific solicited system AEs (parotid/salivary gland swelling, fever and rash) will be collected for 30 days following the MMR and VV vaccine administration at Visit 5.

The following solicited adverse events are included in the Subject Diary. Each adverse event is to be assessed using the scoring system reported in the tables below.

The collected data will be entered into the Subject Diary. Please see Section [5.6.16.1](#) for more detail.

7.1.3.1. **Solicited local adverse events (*administration site event*)**

Solicited local AEs (*administration site event*) will be collected following each study vaccine, by site of administration.

- Hardness of skin at injection site (*Induration at injection site*),
- Swelling of skin at injection site (*Swelling at injection site*),
- Redness at injection site (*Erythema at injection site*),
- Tenderness or discomfort to the touch at injection site (*Tenderness at injection site*).

In the eCRF, solicited local AEs (*administration site event*) occurring within 30 minutes after vaccination are described as mentioned within brackets.

7.1.3.2. **Solicited systemic adverse events**

- Decreased eating (*Change in eating habits*),

- Increased sleepiness (*Sleepiness*),
- Vomiting/throwing up (*Vomiting*),
- Loose stools/diarrhea (*Diarrhea*),
- Irritability (*Irritability*),
- Persistent/continuous crying (*Persistent crying*),
- Rash (only after MMR and VV administration at Visit 5),
- Parotid/salivary gland swelling (only after MMR and VV administration at Visit 5),
- Fever, defined as body temperature $\geq 38.0^{\circ}\text{C}/100.4^{\circ}\text{F}^*$.

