7.1.3.3. Other solicited adverse events

Solicited local (**administration site**) and systemic AEs that continued beyond day 7 after vaccination will not need to be entered as an AE in the AE eCRF or the subject's source document. They will be collected via the eDiary.

Note: Any solicited adverse event that meets any of the following criteria must be entered into subjects' source document (see Section 10.2) and also as an adverse event on the Adverse Event eCRF:

- Solicited local or systemic adverse event that leads to a visit to a healthcare provider (medically attended adverse event, see Section 7.2.3.4).
- Solicited local or systemic adverse event leading to the subject withdrawing from the study or the subject being withdrawn from the study by the investigator (adverse event leading to withdrawal).

Solicited local or systemic adverse event that otherwise meets the definition of a serious adverse event (see Section 7.1.2).

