- Other procedure not required by the protocol.
- Lack of efficacy of the vaccine(s), if applicable.
- Erroneous administration.
- Other cause (specify).

All AEs, regardless of severity, will be monitored by a qualified healthcare professional until resolution or until the investigator assesses them as chronic or stable, and recorded in the subject's records. All subjects experiencing AEs – whether considered associated with the use of the study vaccine(s) or not – must be monitored until symptoms subside and any abnormal laboratory values have returned to baseline, or until there is a satisfactory explanation for the changes observed, or until death, in which case a full pathologist's report should be supplied, if possible. The investigator's assessment of ongoing AEs at the time of each subject's last visit should be documented in the subject's medical chart and eCRF.

In addition, SAEs will be evaluated by the Sponsor or designee for "expectedness." An unexpected AE is – for example – one that is not listed in the current Summary of Product Characteristics or the Investigator's Brochure or an event that is by nature more specific or more severe than a listed event.

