- Any occurrence of an event listed in the exclusion criteria which must be always reassessed by the investigator before administration of the ~~second~~ **next** dose of study vaccine. Refer to Section 4.2.

Time period of recording of concomitant vaccinations (Section 6.7.1 Recording of concomitant medications/products and concomitant vaccinations)

Criteria updated to record concomitant vaccinations from birth, rather than 14/28 days prior to first study vaccine dose.

- Any concomitant vaccination administered in the period starting ~~from birth 14 days (or 28 days for live attenuated vaccines)~~ before the first dose of study vaccine(s) and ending at the last study visit (Day -14 to Day 661).

Recording of solicited AEs only via eDiary (Section 7.1.1 Definition of an adverse event)

Solicited AEs are derived from organized data collection systems, such as Subject Diaries, ~~or interview.~~

Recording of solicited AEs in the eCRF (Section 7.1.3.3 Other solicited adverse events)

Solicited local and systemic AEs that continued beyond day 7 after vaccination will not need to be entered as an AE in the AE eCRF or the subject's source document. They will be collected via the eDiary.

Note: Any solicited adverse event that meets any of the following criteria must be entered into subjects' source document (see Section 10.2) and also as an adverse event on the Adverse Event eCRF:

- ~~Solicited local or systemic adverse event that continues beyond day 7 after vaccination.~~

- Solicited local or systemic adverse event that leads to a visit to a healthcare provider (medically attended adverse event, see Section 7.2.3.4).
- Solicited local or systemic adverse event leading to the subject withdrawing from the study or the subject being withdrawn from the study by the investigator (adverse event leading to withdrawal).

Solicited AEs ongoing after 7 days post-vaccination

Solicited AEs that are ongoing after the 7-day reporting period will continue to be recorded in the eDiary until resolution or up to 30 days post-vaccination (ie, recording period for unsolicited AEs).

Table 5 List of Study Procedures: Footnote added as *¹¹ **Solicited AEs that are ongoing after the 7-day reporting period will continue to be recorded in the eDiary until resolution.***

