### 5.4.2.2. Duration of Solicited Adverse Events

Duration of a solicited adverse event will be calculated as follows:  $\text{end date} - \text{start date} + 1$ . The duration will be derived assuming that the solicited adverse event occurred continuously from the first day to the last day the event was reported regardless of how many days the event was documented in between.

Statistics (i.e. mean, median minimum, maximum, quartiles) on the duration in days of solicited local (administration site) and systemic adverse events post vaccination will be reported by timepoint and overall, by each solicited reaction, for each vaccine group.

Statistics (i.e. mean, median minimum, maximum, quartiles) on the duration in days of solicited local (administration site) and systemic adverse events post any vaccination will be reported by each solicited reaction, for each vaccine group.

Statistics (i.e. mean, median minimum, maximum, quartiles) on the day of onset of solicited local (administration site) and systemic adverse events post vaccination will be provided by timepoint, by each solicited reaction, for each vaccine group.

Statistics (i.e. mean, median minimum, maximum, quartiles) on the day of onset of solicited local (administration site) and systemic adverse events post any vaccination will be provided by each solicited reaction, for each vaccine group.

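### SAP 5.4.2.2 treats solicited reactions still present at the last diary entry as completed, so their durations are right-censored without being marked as such

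*Protocol*

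**What the plan says.** **Recording.** Current Protocol 7.1.3.3 (the same words appear in the Amendment 3 log in Appendix C) says of solicited reactions "that continued beyond day 7 after vaccination will not need to be entered as an AE in the AE eCRF or the subject's source document"; the eDiary is the place where such events are collected. Three kinds must still go on the AE form: "Solicited local or systemic adverse event that leads to a visit to a healthcare provider"; "Solicited local or systemic adverse event leading to the subject withdrawing from the study"; and "Solicited local or systemic adverse event that otherwise meets the definition of a serious adverse event".

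**When the diary stops.** Protocol 7.1.3 sets a 7-day collection, "with ongoing solicited AEs collected until resolution or day 30, whichever occurs first"; the footnotes to Tables 5 and 13 agree. Under 5.6.13 and 5.6.14.1 the first device is collected at Visit 4 and the second at Visit 6. Table 6 allows each of those visits 21 to 60 days after the preceding dose.

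**Outcome and follow-up.** Protocol 7.2.3.3 provides outcome categories for unsolicited AEs, including SAEs, and does not mention other solicited AEs. Protocol 7.2.3.2.2, by contrast, states: "All AEs, regardless of severity, will be monitored by a qualified healthcare professional until resolution", or until judged chronic or stable, with recording in the subject's records. Protocol 7.4.1.1 has AEs designated as unresolved reviewed until 30 days after the last vaccination.

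**Analysis.** SAP 5.4.2.2 defines duration as end date minus start date plus 1, assuming that the event "occurred continuously from the first day to the last day the event was reported". It then reports mean, median, minimum, maximum and quartiles by reaction and group, by timepoint and across vaccinations. It has no rule for an event still present at the last entry.

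**The concern.** A diary that closes on a fixed day, or on the day the device is returned, censors any reaction that has not yet ended. The last reported day is then a lower bound on the end date. SAP 5.4.2.2 uses it as the end date itself, so a reaction that stopped on Day 30 and one that was still present on Day 30 give the same number in the tables.

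At stake are the descriptive duration tables for every solicited reaction, dose and group. They support the tolerability part of the primary safety objective but are not its endpoints. The longest reactions are the ones shortened, and the table gives no sign that this has happened. Sites also have two sets of instructions on whether such an event must be followed and recorded after the diary closes.

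**Working it through.** The plan states no figure to reproduce, so the check applies the SAP's rule to the diary limits.

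**Inputs**
- Day numbering: the day of vaccination is Day 1, so a visit k days after vaccination falls on Day k + 1.
- Diary end: resolution or Day 30 (Protocol 7.1.3, Tables 5 and 13).
- Device return: Visit 4 after dose 3 and Visit 6 after dose 4, each 21 to 60 days after the dose (Table 6). After doses 1 and 2 the parent keeps the device, so only Day 30 applies.
- Duration = end date − start date + 1 (SAP 5.4.2.2).
- Temperature is entered in the evening (Protocol 5.6.16.1). I take the last full entry to be the evening before return.

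**Longest duration that can be recorded**

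| Device returned | Return day | Last full entry | Onset Day 1 | Onset Day 7 |
|---|---|---|---|---|
| 21 days after dose | Day 22 | Day 21 | 21 − 1 + 1 = 21 | 21 − 7 + 1 = 15 |
| 30 days after dose | Day 31 | Day 30 | 30 − 1 + 1 = 30 | 30 − 7 + 1 = 24 |
| 60 days after dose | Day 61 | Day 30 | 30 | 24 |

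A return at 21 days loses up to 30 − 21 = 9 diary days. If an entry is made on the day of return, the first row's cap for onset on Day 1 becomes 22 days.

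**Example.** A reaction lasting 45 days from Day 1 is analysed as 30 days (short by 15), or as 21 days with a return at 21 days (short by 24).

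**Effect on the mean, by assumption only.** Suppose a share f of reactions is still present on Day 30 with true duration T, and all others last 2 days.
- Mean under the SAP rule = 2(1 − f) + 30f.
- True mean = 2(1 − f) + Tf.
- f = 1%, T = 45: 2.28 against 2.43, understated by 0.15/2.43 = 6%.
- f = 2%, T = 90: 2.56 against 3.76, understated by 1.20/3.76 = 32%.
- f = 5%, T = 90: 3.40 against 6.40, understated by 3.00/6.40 = 47%.

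In all three cases the median is 2 days under either calculation, and the reported maximum is 30.

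**The protocol sections side by side.** Protocol 7.1.3.3 says that these events "will not need to be entered as an AE in the AE eCRF or the subject's source document". Protocol 7.2.3.2.2 requires all AEs to be followed and recorded in the subject's records. Protocol 7.4.1.1 reviews events carrying an unresolved designation, but 7.2.3.3 supplies such designations only for unsolicited AEs. A site cannot tell from these sections which instruction governs a persistent, non-serious, unattended solicited reaction.

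**The case against.** The strongest reply is that the protocol has several other routes by which a persistent reaction can be captured. The wording of 7.1.3.3 lifts a requirement; it does not forbid entry, and three kinds of event must still be entered. Protocol 5.6.7 sends abnormal findings from a symptom-directed examination to the AE form. Section 5.6.14.1 asks for relevant findings at Visits 4 and 6 to be documented in the source and eCRF. Section 7.2.3.2.2 requires follow-up of all AEs and a note of those ongoing at the last visit, and 10.2 sends new safety information reported at a visit to the AE page.

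That disposes of some stronger readings. A reader might infer that these reactions are recorded nowhere after the diary closes and can have no outcome; the routes above do not support that. A reader might also infer that the SAP reports them as resolved. It assigns no outcome, only an end day.

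The reply does not meet the duration point. SAP 5.4.2.2 does not say that an end date obtained by any of these routes replaces the last reported day. SAP 5.4.2.3 gives precedence to the investigator's assessment when two exist for the same solicited event, but it does not address an end beyond the diary.

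Two further replies have weight. Stopping at Day 30 matches the collection period for unsolicited AEs and is a defensible design choice; the point here is how the analysis treats events that reach the limit. Protocol 1.1 also describes most infant reactions in earlier studies as mild or moderate and transient, so the number affected may be small.

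**Conclusion.** The point holds for the duration summaries. As written, SAP 5.4.2.2 analyses right-censored durations as completed ones. The maximum is capped at 30 days, or about 21 to 22 days for a diary returned 21 days after dose 3 or 4, and means can be understated. Medians would probably not move. The 6% to 47% range for the mean rests entirely on assumed shares and durations; the documents give no rate of unresolved reactions, so the actual bias is unknown and could be negligible.

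Two wider conclusions should not be drawn:
- A reader might infer that the primary safety results are biased. The primary solicited endpoints are percentages of subjects with an event within 7 days (30 days for parotid swelling, fever and rash after dose 4). A long reaction counts once whatever its recorded length, so the duration rule does not touch them.
- A reader might infer that the contrast between groups is compressed. That would need more unresolved reactions in one group, which the documents do not show, and SAP 5.4.2.2 specifies no between-group comparison of duration.

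This is a cheap improvement to descriptive tables, together with an inconsistency between protocol sections that needs to be resolved.

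**What to change.** **SAP 5.4.2.2.** Flag each solicited AE present at the last diary entry. Report the number and percentage flagged by event, dose and group. Show their durations as censored, for example as longer than 30 days or as ongoing at diary return. Where a later end date is already on the AE eCRF, use it.

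**Protocol.** Reconcile 7.1.3.3 and 7.2.3.3 with 7.2.3.2.2 and 7.4.1.1, so that it is clear whether a solicited AE still present when the diary closes is to be followed and recorded to resolution, and where.

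**Cost.** The SAP change needs one extra table column and a little programming, and works from diary data already held. The protocol change has limited reach. The current SAP is dated June 2025, and the Amendment 7 rationale of October 2022 already expected more than 700 of 1200 subjects to have 12 months of follow-up after the last dose. New wording cannot recover outcomes for subjects already past Day 30, so the SAP flag is the part with practical value.
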